7.1 DEMOGRAPHIC AND OTHER BASELINE CHARACTERISTICS

7.2 CONCOMITANT DISEASES AND MEDICATION

Only descriptive statistics are planned for this section of the report. Analyses of concomitant diseases and medication will be based on the RS.

Concomitant diseases (i.e., baseline conditions) will be coded according to the most recent version of MedDRA.

Concomitant medication will be coded according to the most recent version of the World Health Organisation – Drug Dictionary.

Concomitant non-drug therapy will be coded according to the most recent version of MedDRA.

Characteristics of the trial disease, such as the disease diagnosis and the type of extra-intestinal diagnoses which are present at start of the study, as well as the occurrence of any prior surgery for ulcerative colitis will be descriptively summarized by treatment. During the course of the study, any changes in the pre-existing extra-intestinal diagnoses (improved or worsened) as well as the development of newly diagnosed extra-intestinal diagnoses will also be summarized.

A medication/non-drug therapy will be considered concomitant to treatment, if it

- is ongoing at the start of trial treatment or
- starts within the on-treatment period (see [Section 6.1](#) for a definition of study analysis phases).

Concomitant medication use (excluding rescue medication, historical medication for UC, and background medication) will be summarised by treatment with frequency and percentage of patients by preferred name. Summaries will be presented for

- concomitant medication taken any time prior to the Week 12 visit (for any patient with a missing Week 12 visit, available data will be summarized up to the end of the Week 12 time window, see [Table 6.7: 1](#)).

The frequency and percentage of patients with historical medication for UC will be displayed, and by number of previous biologic medication used, by number of previous TNF α antagonists used, and by worst reason for discontinuation in the order of lack of initial response, loss of response, intolerance and other. The identification of biologic medication and TNF α antagonists medication will be based on medical review.

The frequency and percentage of patients taking any background medication for UC will be tabulated by type of background therapy, i.e, corticosteroid versus non-corticosteroid. The identification of corticosteroid medication will be based on medical review. Further displays regarding changes in background medication during the on-treatment period are summarized in [Section 7.6.4](#).

Use of rescue medication will be summarised separately (see [Section 7.6.4](#)).

Concomitant use of non-drug therapies will be summarised with frequency and percentage. Summaries will be presented for

- concomitant non-drug therapies taken any time prior to the Week 12 visit (for any patient with a missing Week 12 visit, available data will be summarized up to the end of the Week 12 time window, see [Table 6.7: 1](#)).

7.3 TREATMENT COMPLIANCE

Only descriptive statistics are planned for this section of the report.

Treatment compliance will be summarised overall and by visit via total volume infused (as a % of planned) for the RS using descriptive statistics (N, mean, SD, minimum, median, maximum). The volume infused (as a % of planned) is defined as the volume infused at a visit (in ml as recorded in the eCRF), divided by 100 ml (the volume the patient should have received), times 100. If at least 100 mL has been infused, then it is assumed that the full planned dose has been administered, i.e. compliance is 100%.

For the patients who discontinued the study treatment prematurely, only the scheduled visits before premature discontinuation will be used for the calculation of overall compliance.

The number and percentage of patients with the following overall compliance categories will be presented:

- "<50% of planned",
- "50 to <80% of planned"
- "80 to 100% of planned".

The number of patients who received a dose will also be tabulated per visit.

7.4 PRIMARY ENDPOINT

The Multiple Comparison Procedures and Modeling (MCP-Mod) approach ([10](#), [11](#)) is implemented in two main steps: (1) trial design stage; (2) trial analysis stage. The procedures for the trial design stage, including the selection of candidate models covering a suitable range of dose-response shapes and sample size and power calculations, are provided in the CTP Section 7.3.1 and 7.7. The procedures for the trial analysis stage are specified below.

The primary endpoint of the clinical remission is binary in nature. The estimate of response rate from each dose group is obtained via logistic regression without intercept. In case 0 event is observed in one of the dose groups, a penalized regression based on the Firth's bias reduction method ([21,22](#)) will be used. The subsequent MCP-Mod analysis are based on the response rate on the logit scale.

The doses which are included in Part 1 are placebo, and BI 655130 300 mg SD, 450 mg q4w, and 1200 mg q4w. The primary dose-response analysis of the clinical remission, based on the RS, will use MCP-Mod, and each dose regimen will be described via the appropriate q4w regimen administered over the 12 week treatment period (i.e. 300 mg SD will be approximated by 100 mg q4w; 450 mg q4w and 1200 mg q4w doses will remain unchanged) under the assumption that the cumulative concentrations over time (AUC) and thus the cumulative total dose is the key driver of the efficacy response in the modelling part of MCP-Mod. The response rate for each dose group using NRI as the primary missing data handling approach (see [Section 6.6](#)), as well as the variance-covariance matrix for the primary endpoint are estimated by the data.

The multiple comparison procedure will then be implemented using optimal contrast tests which control the family-wise type I error rate at a one-sided $\alpha = 0.20$. The optimal contrasts corresponding to the candidate models are calculated as in the trial design stage and shown in [Table 7.4: 1](#). In the trial analysis stage, these optimal contrasts will be updated using the expected model means from the candidate set and the estimated variance-covariance matrix from the collected data. The updated contrast coefficients will be described in the final CTR.

Table 7.4: 1 Contrast coefficients

Model	Contrast coefficients for dose			
	Placebo	300 mg BI SD	450 mg BI q4w	1200 mg BI q4w
Linear	-0.395	-0.352	-0.096	0.843
E _{max}	-0.858	0.178	0.325	0.355
Exponential	-0.304	-0.300	-0.261	0.866
Logistic	-0.525	-0.450	0.336	0.639
Sigmoid E _{max}	-0.591	-0.370	0.319	0.642

Note: BI= BI 655130; SD= single dose; q4w= once every 4 weeks.

Proof of concept (PoC) is established if at least one dose-response model is statistically significant, thereby rejecting the null hypothesis of a flat dose-response curve and indicating a benefit of BI 655130 over placebo. Once PoC has been established, then subsequently, it will be tested whether at least one dose of BI 655130 in Part 1 achieves a clinical remission rate at Week 12 ≥ 0.16 superior to placebo (i.e. the maximum anticipated effect of BI 655130 for achieving the primary endpoint, based on the best fitting monotonic dose-response model).

Once the significance of a dose-response signal is established, the dose-response profile and the target dose can be estimated using the best-fitting dose-response model. All significant dose-response models will be re-fitted to the data without any parameter assumptions to generate a set of new estimates of the model parameters from the data. The final dose-response model will be obtained via the model with the smallest Akaike Information Criterion (AIC) (the smaller the AIC value the better the model fit). Estimates for the dose groups will be calculated and will be based on the final dose-response model.

R code to perform the evaluations is available in [Section 9.4](#).

[figure not shown]
Graphical displays of the proportion of patients with clinical remission (including 95% confidence interval) based on the final fitted dose-response model will also be presented.

For the purpose of further model refinement, MCP-Mod will be repeated on the primary endpoint but with an extended set of shapes including the original candidates (i.e. addition of

inverse u-shape). To this end, a quadratic dose-response shape that assumes the maximum effect is obtained at the 800mg q4w dose will be included in addition to the others.

Additionally a sensitivity analysis based on model averaging across the statistically significant models may be conducted in order to assess the robustness of the chosen primary approach. Model averaging will be based on parametric bootstrap approach by sampling from the multivariate normal distribution underlying the logistic regression estimates and then fitting each of the models to each of these samples ([11](#), [12](#)).

Furthermore, covariates may be taken into account in further sensitivity analyses, i.e. inclusion of stratification parameters. R code is also available in [Section 9.4](#). Please see [Table 7.4: 2](#) for a complete summary of primary and sensitivity analysis for the primary endpoint based upon the different methods for handling of missing data, and other strategies for assessing the robustness of the treatment effect.

[figure not shown]
[figure not shown]

Table 7.4: 2 Summary of all analysis to be performed for primary endpoint

Summary of analysis			
Analysis	Analysis set	Imputation Approach	Analysis model
Primary analysis	RS	NRI	MCP-mod

Note:

For MCP-Mod approach, best fitting model is used and no covariates adjustment is applied, unless otherwise specified.

Standard approach of SFS/RBS calculation (see [Section 9.2.1](#)) is applied unless otherwise specified.

For explanation of the different approaches with regard to missing data see [Section 6.6](#).

NRI = No Response Imputation

MI = Multiple Imputation

MI-NRI = Combined MI and NRI approach

OC = observed cases

A forest plot which displays the risk differences versus placebo (and corresponding 95% confidence intervals) will be produced for the primary analysis and other sensitivity analyses on the primary endpoint in a single display. A separate display will be used to illustrate the subgroup effects on the primary endpoint.

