#### Linear

Emax: assumes 90% of the maximum effect is achieved at 300 mg SD dose

Exponential: assumes 1% of the maximum effect is achieved at 300 mg SD dose

Logistic: assumes 30% of the maximum effect is achieved at 300 mg SD dose and 85% of the maximum effect is achieved at 450 mg q4w dose

Sigmoid Emax: assumes 30% of the maximum effect is achieved at 300 mg SD dose and 75% of the maximum effect is achieved at 450 mg q4w dose

Note that the actual shapes are applied on the parameter scale (logit for binary data) according to Pinheiro et al. [[R15-4293](#)] and that the q4w dose is used as model parameter.

[figure not shown]

Figure 7.3.1: 1: Shape of the considered dose response patterns for the MCPMod analysis

PoC is established if at least one dose response pattern is statistically significant, rejecting the null hypothesis of a flat dose response relationship on clinical remission at week 12 jointly for each of the candidate dose response models, with a contrast test controlled for the family-wise type I error rate at a one sided  $\alpha = 20\%$ .

If PoC is established, the statistically significant model(s) from the above candidate set are refitted to the data to generate new estimates for all model parameters.

The statistically significant model with the lowest Akaike Information Criterion (AIC) value will be determined as the best fitting model and will be used for characterization of the dose-response curve.

The choice of two target doses to be investigated in Part 2 of the trial – the confirmatory trial part – is described in [Section 3.1.2](#). The maximum effective dose, as well as the selection of the two pre-specified doses for testing in Part 2, will be based on the modelled efficacy estimates. Only doses within the dose range investigated (0 mg - 1200 mg q4w) will be considered.

If considered necessary and for the purpose of further model refinement, MCPMod might be repeated on the primary endpoint but with an extended set of shapes including the original candidates. Additionally a sensitivity analysis based on model averaging across the statistically significant models may be conducted in order to assess the robustness of the chosen primary approach. Furthermore, covariates may be taken into account in further

sensitivity analyses, i.e. inclusion of stratification parameters. Details of these analyses will be described in the TSAP.

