## 7.7 DETERMINATION OF SAMPLE SIZE

The study is intended to show a benefit of BI655130 (SPESOLIMAB) over placebo in terms of the difference in proportion of patients achieving clinical remission at Week 12 in both Parts 1 and 2.

### 7.7.1 Sample size determination for Part 1

The aims of Part 1 are two-fold. A first aim is to show a significant non-flat dose-response across the different doses of BI655130 (SPESOLIMAB) and placebo assuming a higher rate of remission on BI655130 (SPESOLIMAB) versus Placebo of 0.20. Subsequently, at least one modelled dose within the (total) dose range considered [0 mg, 1200 mg q4w] should show a benefit of at least 0.16 (see rationale below) in the proportion of patients achieving clinical remission at week 12 compared to placebo for demonstration of PoC (and subsequent Go decision). In cases where the benefit compared to placebo is less than 0.16 but at least 0.11 then a more detailed analysis of the part 1 results (e.g. subgroup analyses, PK/PD analyses, biomarker analyses) will be done in order to define the optimal path forward. Assumptions for the efficacy of the selected doses are provided in the table below.

For placebo, the proportion of patients who achieve clinical remission when a centrally-read endoscopy is used is typically very low [[R17-2467](#)]; therefore, for Placebo, a fixed rate of 15% of patients achieving clinical remission at week 12 will be considered for sample size planning in this trial.

Based on these assumptions and the planned sample size of 160 (= 40:40:40:40) the success probability (achieved when the proportion of patients achieving clinical remission at week 12 on a dose of BI655130 (SPESOLIMAB) exceeds the placebo effect by 0.16) is approximately 66% for the base case where a maximum difference to placebo of 0.20 is assumed (0.35, 0.30, 0.25 vs 0.15 for clinical remission rates at week 12 of BI655130 (SPESOLIMAB) high to low doses and placebo respectively). In the case that there is no treatment benefit, the false positive probability is limited by the  $\alpha$ -level for the significance testing of the non-flat dose-response curve of 20% (one-sided).

The following [Table 7.7.1:1](#) provides success probabilities under different scenarios, whereby success is defined as 1) Significant non-flat dose-response achieved AND 2) Treatment benefit of at least 'delta' compared to placebo for at least one modelled dose within the considered dose range.

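### The model-based 95% intervals in the Part 1 dose-response analysis show no allowance for AIC model selection; if they are conditional on the selected model, they under-cover below 1200 mg

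*SAP*

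**What the plan says.** Protocol 7.3.1 (Part 1) and SAP 7.4 test five candidate shapes: linear, Emax, exponential, logistic and sigmoid Emax. The tests are "optimal contrast tests which control the family-wise type I error rate at a one-sided" level of 0.20. The significant models are then refitted and one is kept: "The statistically significant model with the lowest Akaike Information Criterion (AIC) value will be determined as the best fitting model". SAP 7.4 takes the dose-group estimates from that model and plots the remission proportions from it, "including 95% confidence interval) based on the final fitted dose-response model will also be presented".

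For robustness, SAP 7.4 offers: "Additionally a sensitivity analysis based on model averaging across the statistically significant models may be conducted". It describes this as a parametric bootstrap that samples the group estimates and refits each model in every sample.

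SAP 7.4 also plans "A forest plot which displays the risk differences versus placebo (and corresponding 95% confidence intervals", for the primary and the sensitivity analyses of the primary endpoint. It does not say whether these differences come from the fitted model or from raw proportions. The note under Table 7.4:2 says that MCP-Mod rows use the best-fitting model. The parallel plot for the secondary endpoints (SAP 7.5.2) is expressly of unadjusted differences.

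Model-free results are planned too. Protocol 7.3.1 provides unadjusted risk differences with 95% intervals, and SAP 7.5.2 indicates that the Newcombe method applies to the primary endpoint.

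**The concern.** An interval computed as if the selected model had been fixed in advance leaves out the uncertainty of the selection. Here that uncertainty is large. There are four dose groups, so the logistic and sigmoid Emax models, with four parameters each, are saturated and AIC rarely chooses them. In practice the choice lies mostly between linear (two parameters) and Emax (three).

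On the modelling scale of 0, 100, 450 and 1200 mg q4w, a linear model fixes the 300 mg SD effect at 100/1200 = 1/12 of the 1200 mg effect on the logit scale, and the 450 mg effect at 450/1200 = 0.375 of it. Protocol 4.1.2 expects 450 mg to be near the plateau and 1200 mg at it. When linear is selected and the truth bends, the difference intervals at the lower doses are both misplaced and very narrow.

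At stake is how the dose-response curve is described in the report and in any authority interactions (SAP Section 3). The report could carry two sets of nominal 95% intervals with very different real coverage, the poorer set attached to the primary analysis.

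**Working it through.** **Inputs.** Size: "the planned sample size of 160 (= 40:40:40:40" (Protocol 7.7.1). Base case: "0.35, 0.30, 0.25 vs 0.15 for clinical remission rates at week 12 of BI655130 (SPESOLIMAB) high to low doses and placebo respectively". Success: a modelled dose must "show a benefit of at least 0.16" over placebo. One-sided alpha is 0.20, and the doses and candidate shapes are those of Protocol 7.3.1 and SAP 7.4. Solving the shape statements gives Emax ED50 11.1; exponential delta 335.6; logistic ED50 214.9 and delta 135.6; sigmoid Emax ED50 192.5 and h 1.29.

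**Method.** 10,000 trials were simulated per scenario. Each had group logits (Firth correction if a group had no events), contrasts updated with the estimated variances, generalised least-squares fits with customary parameter bounds (an assumption), and the lowest AIC among significant models. With v = p(1-p) and V the covariance of the fitted logits, the conditional interval is p_d - p_0 ± 1.96 × sqrt(v_d² V_dd + v_0² V_00 - 2 v_d v_0 V_d0). Coverage is counted in trials with proof of concept, because only those have a final model.

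**The plan's own figure first.** Table 7.7.1:1 at delta 0.16, simulated against stated: + 0.669/0.672; +M+ 0.750/0.746; +L- 0.708/0.704; Sub-optimal 0.456/0.460; Minimal 0.266/0.268; No effect 0.022/0.020; ++ 0.898/0.896. All seven agree. The delta 0.11 column does not: the simulation is 2-6 points higher (base case 0.881 against 0.836). This does not drive the result. With alpha 0.15, 0.10 or 0.05, base-case difference coverage at 300 mg SD / 450 mg is 56/55%, 58/57% and 59/58%, against 54/53% at 0.20.

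**One data set by hand.** Suppose the trial observes exactly the base case: 6, 10, 12 and 14 remissions out of 40.
- Logits are -1.735, -1.099, -0.847, -0.619; weights n p(1-p) are 5.1, 7.5, 8.4, 9.1.
- The linear fit is -1.326 + 0.000652 × dose. Its weighted residual sum of squares is 0.853 + 0.197 + 0.288 + 0.051 = 1.39, so AIC = 1.39 + 2×2 = 5.39.
- The best Emax fit (ED50 about 91) leaves 0.07, so AIC = 0.07 + 2×3 = 6.07. No three-parameter model can score below 6, and no four-parameter model below 8. Linear is selected; its contrast statistic of 1.72 exceeds the critical value of about 1.28.
- Linear-model difference at 300 mg SD: 1.1 points, SE 0.54, interval 0.0 to 2.2. The true difference is 10.
- At 450 mg: 5.3 points, SE 2.81, interval -0.2 to 10.8. The true difference is 15.
- The 450 mg rate interval, 19.3% to 33.2%, does contain the true 30%.
- Newcombe intervals from the same data: -7.7 to 27.1 at 300 mg SD and -3.4 to 32.4 at 450 mg. Both contain the truth.

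**Coverage over repeated trials.** The table gives coverage (%) of the nominal 95% interval for the difference to placebo. The bootstrap columns repeat the AIC selection in each of 300 resamples (446-687 trials per scenario).

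| Scenario | 300 mg SD | 450 mg | 1200 mg | Bootstrap 300 mg SD | Bootstrap 450 mg |
|---|---|---|---|---|---|
| + (base) | 54 | 53 | 97 | 90 | 94 |
| +M+ | 67 | 67 | 95 | 93 | 97 |
| +L- | 44 | 45 | 96 | 87 | 93 |
| Sub-optimal | 40 | 71 | 97 | 83 | 93 |
| Minimal | 48 | 94 | 95 | 60 | 95 |
| ++ | 73 | 74 | 95 | 96 | 97 |

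AIC-weighted averaging is within about 3 points of the bootstrap columns. Newcombe intervals cover 94-96% at 300 mg SD and 450 mg in all six scenarios. Intervals for the remission rates themselves cover 78-94% at 450 mg and 89-98% in the other three groups. Two further implementations gave difference coverage of 50/51% and 54/52% (base), 39/44% and 43/44% (+L-), and 67/72% and 71/73% (++). One of them also gave 40/69% (Sub-optimal) and 50/90% (Minimal). The conditional figures should therefore be read to within about 6 points.

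**Cause.** Linear is selected in 24-67% of proof-of-concept trials with an effect. Used throughout in the base case, its difference interval covers 0% at 300 mg SD and 3% at 450 mg; Emax used throughout covers 80% and 94%. If the truth is a candidate shape with a high-dose rate of 0.35, coverage at 300 mg SD / 450 mg is 92/93% (linear), 82/79% (Emax), 32/43% (exponential), 71/47% (logistic) and 44/44% (sigmoid Emax).

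**The case against.** The strongest case against has four parts.

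First, the SAP sentence that promises model-based intervals concerns remission proportions, where under-coverage is mainly at 450 mg and moderate. The low figures belong to differences, and the text never says that the forest plot takes these from the model. This stands. The note under Table 7.4:2 suggests a model-based row, but does not settle it.

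Second, the interval method is not visible. Section 9.4 is not public, and Table 7.4:2 shows a single row although it is described as a complete summary, so mandatory model averaging may sit in text that cannot be seen. This also stands, and it is why the point is conditional.

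Third, model-free Newcombe differences with proper coverage are planned, and an extended candidate set will be run. The Newcombe differences let a reader check the model-based figures, but they do not correct the intervals attached to the fitted curve.

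Fourth, nothing is decided on these intervals. The Go rule compares a modelled point estimate with 0.16, and its success probabilities reproduce with the selection step built in. SAP Section 3 says that a seamless Part 2 is no longer viable. A reader might infer that proof of concept or the choice of doses is compromised; the documents do not support that.

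It is also fair to say that the bootstrap is no complete cure. Part of the problem is misspecification, and at 300 mg SD it still covers only 83% in Sub-optimal and 60% in Minimal.

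**Conclusion.** The point holds in conditional form and should be fixed; it is not a must-fix. If the plotted intervals are conditional on the AIC-selected model, those for the 450 mg rate cover about 78-94% in the scenarios with an effect. If the primary forest-plot row is model-based as well, difference intervals cover about 40-73% at 300 mg SD and 45-94% at 450 mg.

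A reader might infer that the plan's intervals in general cover only 40-70%. That goes too far: the figure applies to model-based differences only and depends on the scenario. Coverage is about 95% at 1200 mg, and 92-93% at the two lower doses if the truth is linear.

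The result assumes delta-method intervals with the selected model held fixed, least-squares fits with customary bounds, and counting only trials that reach proof of concept.

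**What to change.** In SAP 7.4, state how the model-based interval is formed. For the parametric-bootstrap model averaging, change *may be conducted* to *will be conducted*, with selection or averaging repeated in every sample. Take the 95% intervals in the dose-response figure from it, and show the AIC-best curve as an overlay without its own conditional interval. In the forest plot, show the unadjusted Newcombe differences for the dose groups, or label any model-based row as such and give it the bootstrap interval. The contrast test and the Go rule stay as they are.

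The cost is SAP wording, a short bootstrap run of a kind the SAP already describes, and somewhat wider intervals (about 17 to 20 points at 450 mg in simulation). The report should say that the bootstrap interval can still be too narrow at 300 mg SD when the effect is small, and point to the Newcombe interval there. If the code in Section 9.4 already repeats the selection, a sentence saying so is enough for the dose-response figure.
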